
6.2.1.2 Dosage Adjustments, Delays, Rules for Withholding or Restarting, Permanent Discontinuation

Dose reductions of talimogene laherparepvec are not permitted, other than with respect to a reduction in the volume injected due to a disease response.

If a subject experiences any of the following treatment-related toxicities, talimogene laherparepvec administration should be delayed until the toxicity has resolved to at least CTCAE grade 1 or has returned to baseline:

- grade 2 or greater immune-mediated adverse events, with the exception of vitiligo
- grade 2 or greater allergic reactions
- any other grade 3 or greater hematologic or non-hematologic toxicity

Subjects who are receiving talimogene laherparepvec may not receive systemic antitherpetic drugs (eg, acyclovir, valacyclovir, famciclovir), but may receive a topically administered antitherpetic drug more than 20 cm from a talimogene laherparepvec injection site. Dosing should be permanently discontinued if, in the opinion of the investigator, the subject develops clinical evidence of any systemic herpes infection (such as encephalitis or disseminated infection).

If the subject requires corticosteroid dosing of >10 mg prednisone daily (or equivalent) for related toxicities, talimogene laherparepvec dosing must be withheld until the corticosteroid dose has decreased to <10 mg prednisone daily (or equivalent).

All necessary supportive care therapies shall be available to subjects except for those listed in [Section 6.8](#). Talimogene laherparepvec treatment should be continued based on the potential benefit/risk assessment of the subject.

If talimogene laherparepvec treatment is delayed by >1 week, that dose will be deemed to have been missed and the subject will proceed to the next scheduled treatment visit.

If talimogene laherparepvec dosing is delayed by more than 4 weeks from the date of the planned dose (ie, approximately 6 weeks from the previous dose) due to the occurrence of an adverse event that is considered related to talimogene laherparepvec, the subject must be permanently withdrawn from talimogene laherparepvec treatment.

If talimogene laherparepvec dosing is delayed by more than 4 weeks from the date of the planned dose (ie, approximately 6 weeks from the previous dose) for reasons other than treatment-related toxicity, the case must be reviewed by the Amgen medical monitor in conjunction with the investigator to determine if the subject can resume talimogene laherparepvec therapy.

Talimogene laherparepvec is to be permanently discontinued for subjects meeting any of the following criteria:

- The subject, for any reason, requires treatment with another anticancer therapeutic agent for treatment of the study disease (other than the exceptions noted in [Section 6.5](#)). In this case, discontinuation from the treatment occurs immediately upon introduction of the new agent.
- A grade 2 or greater immune-mediated adverse event (with the exception of vitiligo) or allergic reactions attributed to talimogene laherparepvec that would require a dose delay of greater than 4 weeks from the date of the planned dose (ie, approximately 6 weeks from the previous dose).

Note: immune-mediated glomerulonephritis, vasculitis, and pneumonitis, and exacerbation of psoriasis have been observed in subjects receiving talimogene laherparepvec in clinical trials. Most of these subjects had a history of other autoimmune disease and/or prior treatment with agents that offered plausible alternative etiologies, however, immune-mediated adverse events can potentially involve any organ system.

- Any other talimogene laherparepvec-related non-hematologic or hematologic toxicities grade 3 or greater occur that, in the opinion of the investigator, would require a dose delay of greater than 4 weeks from the date of the planned dose (ie, approximately 6 weeks from the previous dose).
- The subject develops clinical evidence of any systemic herpes infection (such as encephalitis or disseminated infection).
- A female subject becomes pregnant or fails to use acceptable method(s) of effective contraception (for those subjects who are able to conceive) while on talimogene laherparepvec treatment.
- A female subject-breast feeds a child while on talimogene laherparepvec treatment.
- Concurrent medical illness that, in the judgment of the investigator, would make continued treatment with talimogene laherparepvec dangerous for the subject.

For additional information related to special warnings and precautions for the use of talimogene laherparepvec please refer to the latest version of the [Talimogene Laherparepvec Investigator's Brochure](#).

6.3 Other Protocol-required Therapies

Surgical radical resection of melanoma lesion(s) aimed to achieve both clinically and microscopically tumor-free margins will be performed at any time during weeks 13 to 18 (Arm 1) or weeks 1 to 6 (Arm 2). Subjects randomized to Arm 1 who stop talimogene laherparepvec prior to week 12 due to disappearance of all injectable tumor lesions, intolerance to talimogene laherparepvec, or any other reason will undergo surgical resection of melanoma lesion(s) or tissue where melanoma was present before achieving CR within 1 to 6 weeks after the last dose of talimogene laherparepvec. If surgery will be performed prior to week 12, the investigator or designee should notify the sponsor's medical monitor as soon as possible. Refer to [Appendix F](#) for surgery guidelines. Details on handling surgical specimens are provided in the Laboratory Manual.

All other protocol-required therapies including topical anesthetics or injectable local anesthetic medications used for pretreatment of the talimogene laherparepvec injection site that are commercially available are not provided or reimbursed by Amgen (except if required by local regulation). The investigator will be responsible for obtaining supplies of these protocol-required therapies. Additional details regarding these protocol-required therapies are provided in the IPIM.

6.4 Concomitant Therapy

Throughout the study, investigators may prescribe any concomitant medications or treatments deemed necessary to provide adequate supportive care except for those listed in [Section 6.8](#).

All prescription and nonprescription concomitant medication administered up to 28 days prior to randomization, on an ongoing basis at randomization, as well as changes in such concomitant medication, and any new concomitant medication taken while the subject is on study, should be recorded on the appropriate case report form (CRF) until 30 days (+15) days after surgery. The therapy name, indication, dose, unit, frequency, start date, and stop date will be collected. Concomitant medications administered 30 (+15) days after surgery for serious adverse events should be recorded as defined in [Section 9.2](#).

Investigators should use supportive care agents in compliance with their respective regional labels. Investigators may not use supportive care agents as part of a separate clinical trial.

6.5 Other Treatment Procedures

Following surgical resection of melanoma lesion(s), adjuvant systemic therapy and/or radiotherapy may be administered at the investigator's discretion and per the institutional standard of care. If adjuvant therapy (systemic and/or radiation therapy; approved or investigational) is planned, this should be reported via IVR during randomization.

If a subject undergoes adjuvant therapy, the investigator or designee should notify the sponsor's medical monitor as soon as possible and the treatment should be recorded in the source document and CRF.

6.6 Medical Devices

Medical devices (eg, syringes, sterile needles, alcohol prep pads), that are commercially available are not usually provided or reimbursed by Amgen (except, for example, if required by local regulation). The investigator will be responsible for obtaining supplies of these devices.

6.7 Product Complaints

A product complaint is any written, electronic or oral communication that alleges deficiencies related to the identity, quality, durability, reliability, safety, effectiveness, or performance of any investigational or non-investigational product(s) or device(s).

Any product complaint(s) associated with an investigational product(s) or non-investigational product(s) or device(s) supplied by Amgen are to be reported according to the instructions provided in the IPIM.

6.8 Excluded Treatments and/or Procedures During Study Period

Subjects must not use any of the following therapies during screening or treatment period:

- other investigational agents or procedures
- concurrent experimental or approved antitumor therapies other than study drug
- chronic oral or systemic steroid medication use at a dose of > 10 mg/day of prednisone or equivalent (with the exception of treatment for adverse events [see [Section 6.2.1.2](#)]). Steroids with low systemic absorption [eg, triamcinolone hexacetonide] injected into a joint space are allowed)
- antiherpetic drugs (eg, acyclovir), other than if topically administered > 20 cm from a talimogene laherparepvec injection site
- Subjects must not schedule any elective surgeries during the treatment period and for at least 30 days after surgical resection of melanoma lesion(s). If a subject undergoes any unexpected surgery during the course of the study, talimogene laherparepvec must be withheld and the investigator or designee should notify the sponsor's medical monitor as soon as possible. A subject may be allowed to resume talimogene laherparepvec if both the investigator and the sponsor's medical monitor agree to restart study therapy.

The exclusion criteria describe other medications and procedures which are prohibited in this study (refer to [Sections 4.1.2](#)).

There are no prohibited therapies and procedures during the postsurgery long-term follow-up period.

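### Sections 6.8 and 6.2.1.2 conflict on antiherpetic drugs: read literally, 6.8 withholds them from an Arm 1 subject with systemic herpes infection between the last dose and surgery

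*Protocol*

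**What the plan says.** Protocol Section 6.8 opens its list of exclusions with "Subjects must not use any of the following therapies during screening or treatment period". One bullet on the list is "antiherpetic drugs (eg, acyclovir), other than if topically administered > 20 cm from a talimogene laherparepvec injection site". The bullet directly above it, on chronic steroids, carries a qualifier that the antiherpetic bullet lacks: "with the exception of treatment for adverse events". Section 6.8 closes by lifting all prohibitions in the long-term follow-up after surgery.

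Section 6.2.1.2 deals with the same drugs in different terms: "Subjects who are receiving talimogene laherparepvec may not receive systemic antitherpetic drugs (eg, acyclovir, valacyclovir, famciclovir"). It allows the same topical use beyond 20 cm. Its criteria for permanent discontinuation include: "The subject develops clinical evidence of any systemic herpes infection (such as encephalitis or disseminated infection").

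Two clauses might have restored access to treatment, but both defer to 6.8. Section 6.2.1.2 says "All necessary supportive care therapies shall be available to subjects except for those listed in" Section 6.8, and Section 6.4 says that "investigators may prescribe any concomitant medications or treatments deemed necessary to provide adequate supportive care except for those listed in" Section 6.8.

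A subject in Arm 1 who stops the virus early, for whatever reason, has surgery 1 to 6 weeks after the last dose (Sections 3.1, 6.3 and 7.2.2). One who completes dosing has surgery in weeks 13 to 18.

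**The concern.** The protocol itself names systemic herpes infection as a reason to stop the virus for good. That is the situation in which an investigator would want to give a systemic antiherpetic, and the two sections that govern the drug do not agree on whether it may be given. One ties the ban to receiving the virus; the other ties it to a study period that continues after the last dose. A site that follows the list of excluded treatments as written would withhold or delay treatment of encephalitis or disseminated infection. A site that treats could find the treatment queried or recorded as a deviation. The matter is one of subject safety and clear instruction to sites, not of the primary analysis.

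**Working it through.** No statistical figure is involved. The check sets the rules side by side and then measures the interval.

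**1. Scope of each ban**

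| | Section 6.2.1.2 | Section 6.8 |
|---|---|---|
| Applies to | Subjects who are receiving the virus | All subjects in screening or the treatment period |
| Drugs | Systemic antiherpetics | Antiherpetics generally |
| Exception | Topical, beyond 20 cm | Topical, beyond 20 cm |
| Exception for adverse events | None stated | None for antiherpetics; one for steroids |
| When the ban ends | Implied: when the subject is no longer receiving the virus | Stated only for long-term follow-up after surgery |

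**2. Is surgery inside the treatment period?** For Arm 1, Section 7.2.2 starts treatment at the first dose and lists surgery among the treatment procedures. Table 2 puts the week 13 to 18 column under Treatment Period and the 30 (+15) day visit under Follow-up. So until surgery is a sound reading of the protocol, though an inferred one. SAP Section 6 defines the treatment period for analysis as running to 30 days after the last dose or surgery, whichever is later. Until surgery is the shorter of the two readings.

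**3. Does another sentence give permission?** Neither supportive-care clause does, because each excludes whatever 6.8 lists. There is a useful contrast. For another anticancer agent, a class that 6.8 also bars, Section 6.2.1.2 provides for its use and says what follows: "In this case, discontinuation from the treatment occurs immediately upon introduction of the new agent". It has no matching sentence for antiherpetics.

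**4. Length of the literal ban**

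Let S be the day of surgery and d the day the infection is recognised, both counted from the last dose. The remaining ban is max(0, S − d).

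- Early stop: S is 1 to 6 weeks, that is 7 to 42 days.
- Dosing completed on day 1 of week 12: the first day of week 13 is (13 − 12) × 7 = 7 days later. The first day of week 18 is (18 − 12) × 7 = 42 days later, and its last day is 42 + 6 = 48 days later. The interval is again about 1 to 6 weeks, or just under 7 weeks at the extreme.

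For S = 7 to 42:

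| d (days) | Remaining ban (days) |
|---|---|
| 0 | 7 to 42 |
| 3 | 4 to 39 |
| 7 | 0 to 35 |
| 14 | 0 to 28 |
| 21 | 0 to 21 |

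The last two rows correspond to the nominal lengths of later cycles (14 days) and of the first cycle (21 days). The recognition days are illustrative, because the documents give none.

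**The case against.** The best answer is that Section 6.2.1.2 is the more specific rule. It limits the systemic ban to subjects receiving the virus, and the same paragraph orders permanent discontinuation for systemic herpes infection. Read together, its ban falls away once dosing stops. The 6.8 bullet repeats the same 20 cm allowance and may be no more than shorthand for it.

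Other text points the same way. Section 6.8 also bars other antitumor therapy, yet Section 3.1 allows other melanoma treatment when the investigator judges it warranted, and 6.2.1.2 provides for another anticancer agent. The 6.8 list is therefore not applied rigidly once dosing stops. Section 8.2.1 counts meeting the 6.2.1.2 criteria among the reasons for removal from treatment, and the glossary does not tie the end of treatment to surgery for such a subject. Section 6.2.1.2 also refers to the Investigator's Brochure for special warnings and precautions; it is not available here and may give treatment advice.

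Most of this stands as evidence of intent. It does not remove the conflict. The narrower wording in 6.2.1.2 grants no permission, 6.8 does not say that its ban ends with dosing, and the supportive-care clauses send the reader back to 6.8. Intent that has to be pieced together from several sections is a weak basis for an urgent treatment decision.

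A further objection is that the interval in days says little, since a subject with encephalitis might not have surgery on schedule and Appendix F leaves surgery to clinical judgment. That is fair. The figures describe the protocol window and do not predict any subject's course.

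**Conclusion.** The point holds as a conflict in scope between two sections of the protocol, probably unintended, and worth fixing because it concerns treatment of a serious infection. Read literally, 6.8 withholds systemic antiherpetics for up to about 6 weeks between the last dose and surgery from an Arm 1 subject with systemic herpes infection, whether dosing was stopped early or completed. This rests on taking the treatment period to run through surgery, as Table 2 and Section 7.2.2 indicate, and on surgery taking place inside its window.

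A reader might infer more: that the protocol deliberately denies treatment, or that an investigator who treats must breach it. The documents do not support that. Section 6.2.1.2 confines its ban to subjects receiving the virus, the end of the treatment period for a discontinued subject is inferred, and other provisions show that 6.8 is not meant to bind in every case after dosing stops. Nor do the documents show harm to any subject or give a rate of systemic infection. The primary endpoint and the sample size are not affected.

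**What to change.** Keep the 6.8 bullet, "antiherpetic drugs (eg, acyclovir), other than if topically administered > 20 cm from a talimogene laherparepvec injection site", and append: *(with the exception of treatment of systemic herpes infection or other serious herpetic adverse events, in which case no further talimogene laherparepvec is given [see Section 6.2.1.2])*.

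The trigger should be the infection, not the act of discontinuing. An exception limited to infection for which dosing was permanently discontinued would miss a subject who has had all six doses and becomes ill before surgery in weeks 13 to 18, since there is no dosing left to stop. The wording should also avoid affirming a ban after dosing that 6.2.1.2 does not impose. Other serious herpetic events are included because a complication such as herpetic keratitis, named in exclusion criterion 209, need not be systemic.

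Sections 6.2.1.2 and 6.4 need no edit, since their supportive-care clauses follow 6.8. The change can go to sites in a clarification letter and into the next amendment. It costs nothing in sample size or analysis.

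There are two small downsides. A subject treated partway through dosing for a serious but non-systemic herpetic event would forgo the remaining doses. And because tumor response is evaluated up to resection and pathological complete response is read on the surgical specimen, either may be affected in the rare subject treated.

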7. STUDY PROCEDURES

7.1 Schedule of Assessments

For Schedule of Assessments refer to [Table 2](#) and [Table 3](#), respectively.

Table 2. Schedule of Assessments for Arm 1 (Talimogene Laherparepvec Plus Surgery)

	Screening ^a		Treatment Period ^b							Follow-up Period ^c	
	≤ 28 days	≤ 3 days	Week 1	Week 4	Week 6	Week 8	Week 10	Week 12	Week 13 to 18	Safety Follow-up 30 (+15) days	Long-term Follow-up Every 3 months (± 30 days) for 3 years then every 6 months (± 30 days) until 5 years after randomization
GENERAL & SAFETY ASSESSMENTS											
Informed Consent	X										
Review of Medical/Surgical History	X										
Demographic Data (sex, age or date of birth, race, and ethnicity)	X										
Review of Eligibility Criteria	X										
Concomitant Medications	X									X	
Adverse and Serious Adverse Events	X									X	
Adverse Events Potentially Related to Treatment with Talimogene Laherparepvec											X
Physical Exam	X		X	X		X			X	X	
Vital Signs	X		X	X		X		X	X	X	
ECOG Performance Status	X			X		X			X	X	
Surgical Safety Evaluation (including wound closure, drain time, and post operation infection)										X	
Subsequent Anticancer Therapy for Melanoma										X	X
Survival											X
LOCAL LABORATORY ASSESSMENTS											
Urine or Serum Pregnancy Test		X								X	
Hematology	X		X		X			X		X	
Chemistry	X		X		X			X		X	
Serum LDH	X										
PT, PTT or aPTT, INR	X										

Footnotes defined on last page of the table

Table 2. Schedule of Assessments for Arm 1 (Talimogene Laherparepvec Plus Surgery)

	Screening ^a		Treatment Period ^b							Follow-up Period ^c	
	≤ 28 days	≤ 3 days	Week 1	Week 4	Week 6	Week 8	Week 10	Week 12	Week 13 to 18	Safety Follow-up 30 (+15) days	Long-term Follow-up Every 3 months (± 30 days) for 3 years then every 6 months (± 30 days) until 5 years after randomization
CENTRAL LABORATORY ASSESSMENTS											
Blood for HSV-1 Antibody			Week 1 (prior to 1 st dose)								
Archived Tumor Tissue for Biomarker Analyses			Submit to central laboratory within 28 days after randomization								
Archived Tumor Tissue for BRAF ^{V600} Mutation Testing			Submit to central laboratory within 28 days after randomization if BRAF ^{V600} mutation status is unknown prior to screening and was not tested at local laboratory								
Tumor Biopsy			X						X		
Blood for Biomarker Development			X		X				X		
Swab of Herpetic Lesion for qPCR			Within 3 days of occurrence of suspected lesion of herpetic origin								
TREATMENT											
Talimogene Laherparepvec Administration			X	X	X	X	X	X			
Surgery									X		
RADIOGRAPHIC IMAGING, CLINICAL, AND HISTOLOGICAL TUMOR ASSESSMENTS											
Radiographic Imaging (CT, PET/CT, MRI)	X							X			X
Clinical Tumor Measurement and Response Assessment	X							X			X
Histological Tumor Assessment of Surgical Specimen ^d									X		

Footnotes defined on next page of the table

Table 2. Schedule of Assessments for Arm 1 (Talimogene Laherparepvec Plus Surgery)

	Screening ^a		Treatment Period ^b							Follow-up Period ^c		
	≤ 28 days	≤ 3 days	Week 1	Week 4	Week 6	Week 8	Week 10	Week 12	Week 13 to 18	Safety Follow-up 30 (+15) days	Long-term Follow-up Every 3 months (± 30 days) for 3 years then every 6 months (± 30 days) until 5 years after randomization	
REPORTING EXPOSURE TO TALIMOGENE LAHERPAREPVEC												
Exposure of Subject's Household member or Caregiver			X	—————▶							X	
Exposure of Subject's Healthcare Provider			X	—————▶							X	
REPORTING PREGNANCY/LACTATION												
Reporting of Pregnancy or Lactation ^e			X	—————▶								

Page 3 of 3

^a For additional information regarding the procedures performed during screening procedures and the timing of the procedures please refer to [Section 7.2.1](#).

^b For additional information regarding the procedures performed during treatment and the timing of the procedures please refer to [Section 7.2.2](#).

^c For additional information regarding the procedures performed during safety follow-up and long-term follow-up and timing of the procedures please refer to [Section 7.2.3](#) and [Section 7.2.4](#), respectively.

^d Surgical specimens will be assessed for presence of viable tumor and tumor margin status for cutaneous and subcutaneous tumor; please refer to [Section 7.2.2](#).

^e Reporting of pregnancy or lactation: If a pregnancy occurs in a female subject, or female partner of a male subject, or a lactation case occurs in a female subject while the subject is taking talimogene laherparepvec and through 3 months after the last dose of talimogene laherparepvec, the case must be reported to Amgen as specified in [Section 9.3](#).

Table 3. Schedule of Assessment for Arm 2 (Surgery Alone)

	Screening ^a		Treatment Period ^b	Follow-up Period ^c	
	≤ 28 days	≤ 3 days	At time of Surgery (Week 1 to 6)	Safety Follow-up 30 (+15) days	Long-term Follow-up Every 3 months (± 30 days) for 3 years then every 6 months (± 30 days) until 5 years after randomization
GENERAL & SAFETY ASSESSMENTS					
Informed Consent	X				
Review of Medical/Surgical History	X				
Demographic Data (sex, age or date of birth, race, and ethnicity)	X				
Review of Eligibility Criteria	X				
Concomitant Medications	X		X	X	
Adverse and Serious Adverse Events	X		X	X	
Physical Exam	X			X	
Vital Signs	X		X	X	
ECOG Performance Status	X			X	
Surgical Safety Evaluation (including wound closure, drain time, and post operation infection)				X	
Subsequent Anticancer Therapy for Melanoma				X	X
Survival					X
LOCAL LABORATORY ASSESSMENTS					
Urine or Serum Pregnancy Test		X		X	
Hematology	X			X	
Chemistry	X			X	
Serum LDH	X				
PT, PTT or aPTT, INR	X				

Footnotes defined on next page of the table

Table 3. Schedule of Assessment for Arm 2 (Surgery Alone)

	Screening ^a		Treatment Period ^b	Follow-up Period ^c	
	≤ 28 days	≤ 3 days	At time of Surgery (Week 1 to 6)	Safety Follow-up 30 (+15) days	Long-term Follow-up Every 3 months (± 30 days) for 3 years then every 6 months (± 30 days) until 5 years after randomization
CENTRAL LABORATORY ASSESSMENTS					
Archived Tumor Tissue for Biomarker Analyses			Submit to central laboratory within 28 days after randomization		
Archived Tumor Tissue for BRAF ^{V600} Mutation Testing			Submit to central laboratory within 28 days after randomization if BRAF ^{V600} mutation status is unknown prior to screening and was not tested at local laboratory		
Tumor Biopsy			X		
Blood for Biomarker Development			X		
TREATMENT					
Surgery			X		
RADIOGRAPHIC IMAGING, CLINICAL, AND HISTOLOGICAL TUMOR ASSESSMENTS					
Radiographic Imaging (CT, PET/CT, MRI)	X				X
Clinical Tumor Measurement and Response Assessment	X				X
Histological Tumor Assessment of Surgical Specimen ^d			X		

Page 2 of 2

^a For additional information regarding the procedures performed during screening procedures and the timing of the procedures please refer to [Section 7.2.1](#).

^b For additional information regarding the procedures performed during treatment and the timing of the procedures please refer to [Section 7.2.2](#).

^c For additional information regarding the procedures performed during safety follow-up and long-term follow-up and timing of the procedures please refer to [Section 7.2.3](#) and [Section 7.2.4](#), respectively.

^d Surgical specimens will be assessed for presence of viable tumor and tumor margin status for cutaneous and subcutaneous tumor; please refer to [Section 7.2.2](#).

